Assessment of Laryngopharyngeal Sensation in Adductor Spasmodic Dysphonia (SD TT)

NCT05158179

Document date: 10/21/21

PI's: [name] MD and [name] MD

Study Protocol and Statistical Analysis Plan

Participant Recruitment

Subjects with adductor type LD (AdLD) were identified and recruited by advertisements and by study clinicians at their institution. Advertisements were physically placed in the UCSF Voice and Swallowing Center clinic and were delivered electronically through the website of the National Spasmodic Dysphonia Association and to area LD (“spasmodic dysphonia”) support groups.

Adults greater than 18 years old with AdLD were included if they received a diagnosis established by a multi-disciplinary evaluation by a fellowship-trained laryngologist and voice-specialized speech-language pathologist. Subjects diagnosed by a physician outside of the study facility were evaluated in-person by a fellowship-trained laryngologist to confirm their eligibility for this study. All patients were required to have history of favorable response to intra-laryngeal botulinum toxin A (BtxA) treatment, as further demonstration of the correct diagnosis of ADLD. This was especially helpful for patients initially diagnosed outside of our center. Subjects with abductor or mixed type LD were not included in the present study due to their low incidence, but concurrent essential tremor (ET) of the vocal tract was accepted.

Patients were also excluded if they had a history of: concurrent laryngeal diseases or conditions other than AdLD+/-ET; bleeding disorder or current anticoagulation use; head and neck radiation; active tobacco use; or drinking more than two alcoholic beverages per day. If laryngopharyngeal lesions and/or masses, impeding abnormal laryngopharyngeal structure(s), or excessive post-nasal drip were noted on laryngoscopy, then examination ceased, and patients were excluded. Prior to testing, subjects also completed symptom-specific patient reported outcome measures (PROMs), including: Reflux Symptom Index (RSI),¹⁸ Voice Handicap Index-10 (VHI-10),¹⁹ Dyspnea Index (DI),²⁰ Cough Severity Index (CSI),²¹ and Eating Assessment Tool-10 (EAT-10).²² These PROMs are standardly collected as part of the routine clinical care for all patients undergoing evaluation at this center and are reported herein for holistic

characterization of these subjects *but not* intended as a reflection or measure of the severity of their AdLD. Lastly, to avoid any potentially confounding physical effects from the injection (e.g., vocal fold edema), no testing was performed in the two weeks immediately following BtxA treatment. For patient convenience and to facilitate maximal enrollment, patients were allowed to undergo testing at any point outside of this post-injection window, although the majority pursued testing immediately prior to a BtxA injection on the same day.

Healthy controls were defined as adults between 18 and 85 years of age without laryngopharyngeal disease and were subject to the same screening and exclusion criteria.²³ Additionally, controls were excluded if they had abnormal patient reported outcome measures (i.e. Reflux Symptom Index (RSI) score > 13, Eating Assessment Tool-10 (EAT-10) score > 2, or Voice Handicap Index-10 (VHI-10) score > 11).

Aesthesiometer Device

As outlined in previous work, modified nylon monofilaments fixed to the end of 5-French open lumen catheters were utilized to deliver tactile stimuli to laryngopharyngeal subsites.¹² The Food and Drug Administration (FDA) has previously ruled the aesthesiometer to be a Nonsignificant Risk (NSR) Device Study (Q190371/S001). Three nylon monofilament sizes (6-0, 5-0, 4-0) were cut to a calibrated length of 30 mm to deliver three distinct tactile stimuli of increasing strength, known as buckling-force. The 6-0, 5-0, and 4-0 monofilaments deliver an increasing mean force of 0.03 g, 0.11 g, and 0.30 g, respectively.¹² An intermediary strength “4.5-0” monofilament was created by using a 5-0 monofilament of 25mm length, which has been demonstrated to have a mean buckling force of 0.19 g.²³

During testing, the monofilaments were passed through the working channel of a flexible ENF-VT2 laryngoscope (Olympus America, Inc., Center Valley, PA) to allow for direct visualization and concurrent stimulation of laryngopharyngeal subsites.

Laryngopharyngeal Sensory Evaluation

All subjects underwent a standard protocol for laryngopharyngeal sensory evaluation. This has been described in detail previously but briefly reviewed again here.^{12,13} Prior to testing, subjects were screened for any recent changes in conditions affecting voice and swallowing to ascertain subjects-maintained inclusion criteria. Three investigators executed laryngopharyngeal testing: 1) one to operate the laryngoscope; 2) one to maneuver the aesthesiometer monofilament; and 3) one to monitor testing, record subjective patient response, and observe cough/gag/swallow responses.

An investigator then examined both nasal passageways with a nasal speculum, selecting the more patent pathway for laryngoscope insertion. The more patent nasal passageway was topically anesthetized with cottonoid pledges soaked in a 50/50 mixture of 4% lidocaine hydrochloride and neosynephrine. The cottonoid pledges were compressed to remove excess liquid to avoid unintentional spillage posteriorly to the nasopharynx and potentially larynx, and left in place for five minutes.

The channeled laryngoscope was then inserted along the inferior meatus towards the posterior nasopharyngeal wall. The 6-0 monofilament was pressed against the posterior nasopharyngeal wall and swiftly removed to establish a perceptual strength of “1”. If subjects were insensate to this stimulation, monofilament size was incrementally increased (i.e., 5-0, 4.5-0, and 4-0) until the stimulus was perceived, to establish this internal anchor. As per the validated, standardized protocol, all AdLD participants were stimulated on the left, allowing maximal visualization of the vocal folds during testing due to camera configuration of the flexible laryngoscope. Only four controls were stimulated on the right side, during earliest phases of testing.

Starting with the 6-0 monofilament, the lateral pyriform sinus (LPS) was presented with the planned stimulus, followed by the aryepiglottic fold (AEF) and the false vocal folds (FVF). (Figure 1) Participants were instructed to raise their hand when the stimulus was detected, and then were asked

by the study team to report a perceptual strength “score,” in comparison to the nasopharyngeal anchor strength of 1. LAR response was observed and recorded by the study team. A negative response was defined as a lack of LAR to two appropriate stimuli. Gag or cough response to stimuli delivery were also recorded, assuming a positive LAR during these observations.

The LPS and AEF were tested in order of increasing stimulus: 5-0, 4.5-0 and 4-0 monofilaments. The false vocal folds (FVF) were tested last, in the same order of increasing monofilament strength. Testing of FVF terminated after the first observed LAR given site sensitivity, assuming positive responses would also be present for increased monofilament strength.

LAR Assessment

Confirmation of LAR was determined using post-hoc frame-by-frame analysis of video recordings. Unilateral or bilateral vocal fold adduction following stimulus delivery was recorded as a positive response. Upon review, stimuli were excluded if they did not produce 10-30% monofilament buckling (as observed by the reviewer), were entrapped by saliva, or could not compress orthogonally to the mucosal surface. Additionally, if line of sight of visualization of vocal fold adduction was obstructed or confounded by phonation, the stimuli were excluded. All stimuli were reviewed by one study investigator with 30% of stimuli reviewed by a blinded second reviewer. Disagreements were reconciled by a blinded third reviewer.

[figure not shown]
Statistical Methods

Patient demographics, clinical characteristics, and sensory outcomes were summarized using descriptive statistics (means, standard deviations (SD), counts, and percentages). Two-sample Mann-Whitney and Fisher exact tests were used to compare strength ratings and LAR rates between AdLD and control groups at specific sites and filament sizes. To assess predictors of LAR, subjective detection, and

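### Strength ratings are compared between groups although the filament defining each subject's 1 can vary; if the anchor mix differs by group, a rating difference may reflect the nasopharyngeal reference

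*Combined protocol and SAP*

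**What the plan says.** The section Laryngopharyngeal Sensory Evaluation sets the reference as follows: "The 6-0 monofilament was pressed against the posterior nasopharyngeal wall and swiftly removed to establish a perceptual strength of" 1. For a subject who does not feel it, "monofilament size was incrementally increased (i.e., 5-0, 4.5-0, and 4-0) until the stimulus was perceived", and the filament then felt serves as the anchor. After each laryngeal stimulus the subject gives a score "in comparison to the nasopharyngeal anchor strength of 1".

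The section Aesthesiometer Device gives the forces: "The 6-0, 5-0, and 4-0 monofilaments deliver an increasing mean force of 0.03 g, 0.11 g, and 0.30 g, respectively". The intermediate 4.5-0 filament "has been demonstrated to have a mean buckling force of 0.19 g".

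Under Statistical Methods, "Two-sample Mann-Whitney and Fisher exact tests were used to compare strength ratings and LAR rates between AdLD and control groups", separately by site and filament size. The visible text there stops mid-sentence as it turns to predictors, and the text that follows was removed before review. Section 3 (Outcome Measures) makes the LAR primary and lists the rating, on a 1–10 scale, as an additional outcome.

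**The concern.** A personal anchor suits comparisons within a subject, such as one site against another. A between-group comparison of raw scores also needs the unit to mean the same in both groups. The Mann-Whitney comparison holds the laryngeal filament fixed but not the anchor filament, and a two-sample rank test has no term through which the anchor could enter.

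If the share of subjects needing a heavier anchor differs between AdLD and controls, the groups may be scoring the same laryngeal stimulus against different references. A difference in ratings could then be read as altered laryngeal sensation when it comes from the nasopharynx. Equal anchor mixes should be checked and not assumed: the groups differ in mean age (60 v 52 years) and in the proportion of women (9 of 13 v 12 of 33), and the anchor is set after topical lidocaine has been applied to the nose.

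**Working it through.** **Inputs from the documents.** Filament forces 0.03, 0.11, 0.19 and 0.30 g (Aesthesiometer Device); 13 AdLD subjects and 33 controls in the results text; ratings 1–10 (Outcome Measures). The documents give no power, sample-size or significance figure for the ratings, so there is none to reproduce. A two-sided 5% level is assumed.

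**Step 1: range of the reference.** Relative to 6-0, the heavier anchors are 0.11/0.03 = 3.7, 0.19/0.03 = 6.3 and 0.30/0.03 = 10 times as strong. One 0.30 g laryngeal stimulus is therefore 0.30/0.03 = 10, 0.30/0.11 = 2.7, 0.30/0.19 = 1.6 or 0.30/0.30 = 1.0 times the subject's anchor.

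**Step 2: force-ratio model (assumed).** Rating = 3 × (stimulus/0.11)^b × (0.03/anchor)^b × log-normal error, rounded and limited to 1–10. Here b is 0.5 or 1, log SD is 0.4, and escalated subjects are split evenly over 5-0, 4.5-0 and 4-0. Before rounding and limits, a 4-0 anchor lowers a rating by a factor of 10^0.5 = 3.2 to 10^1 = 10. With no true laryngeal difference and 4,000 runs per cell, Mann-Whitney rejection rates are:

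| Anchored above 6-0, AdLD v control | b 0.5, 5-0 stimulus | b 0.5, 4-0 stimulus | b 1, 5-0 stimulus | b 1, 4-0 stimulus |
|---|---|---|---|---|
| 0% v 0% | 5.0% | 5.0% | 4.3% | 4.9% |
| 20% v 20% | 4.3% | 4.8% | 5.2% | 4.7% |
| 30% v 10% | 15.0% | 14.7% | 17.7% | 19.4% |
| 50% v 10% | 43.3% | 44.6% | 54.7% | 55.8% |

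At 30% v 10% the false mean difference is −0.4 to −1.2 points, with the more-escalated group rating lower. A version with log SD 0.5 and 2,000 runs gives 10–19% at 30% v 10% and 28–57% at 50% v 10%.

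**Step 3: other models of the anchor (assumed; log SD 0.5, 2,000 runs).**
- All anchors feel equally strong whatever their force: 4–6% rejection at both 30% v 10% and 50% v 10%, so no inflation.
- The anchor is felt in proportion to force above the subject's own threshold (log-threshold SD 1): 14–32% at 30% v 10% and 25–63% at 50% v 10%, with the sign reversed. A subject escalated to a heavier filament feels it only just above threshold, so the reference is weak and laryngeal stimuli are scored higher against it.

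**Step 4: what the remedy does.** Restriction to 6-0-anchored subjects returns 4–5% in the force-ratio model, but this is by construction, since the anchor becomes constant. In the threshold-relative model restriction still rejects 11–33%, because subjects who feel 6-0 still differ in threshold. A rank test stratified by anchor is nominal in the first two models and reduces the inflation in the third without removing it.

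**Step 5: cost in power.** If 30% v 10% are escalated, restriction leaves 13 × 0.7 = 9.1 AdLD subjects and 33 × 0.9 = 29.7 controls. For a 1 SD normal shift (assumed), power falls from about 82% (13 v 33) to 69% (9 v 30). With half the AdLD group escalated (13 × 0.5 = 6.5) it is about 52% (6 v 30).

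**The case against.** The strongest defence is that the escalation rule normalises the scale. A subject reaches a 4-0 anchor only after failing to feel three lighter filaments, so for that subject 4-0 is a faint stimulus, perhaps as faint as 6-0 is to others. If so, all subjects share one perceived unit and nothing is inflated. This is a coherent reading, and it means that neither size nor direction can be asserted. It does not remove the risk: a subject who feels 6-0 may be well above threshold while an escalated subject is near it, so the rule does not fix perceived strength, and it scales laryngeal scores by sensitivity at another site.

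Three further objections stand as limits on the point.
- The documents give no escalation counts. If every subject felt 6-0, the issue disappears.
- Part of the statistical text is unavailable, so an adjustment for anchor in the predictor models cannot be excluded. The point covers only the visible Mann-Whitney comparison.
- Only the additional outcome is affected. Whether the LAR occurs does not depend on the anchor.

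A reader might infer that AdLD subjects probably had heavier anchors, since altered sensation is the study question. The documents do not support this: the sites under study are laryngopharyngeal, and nothing says AdLD changes nasopharyngeal sensation. A reader might also infer that a heavier anchor must lower every later rating. That holds under the force-ratio model but reverses under the threshold-relative one.

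**Conclusion.** The point holds as a conditional risk to the rating comparison. The text establishes that the reference can be any of four filaments spanning a ten-fold range of force, that every laryngeal score is relative to it, and that the visible between-group test does not take it into account. Whether this matters depends on a group difference in anchor mix, on which the documents are silent.

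The false-positive figures rest on assumed psychophysical models, noise and escalation shares, so they show what is possible and do not estimate what happened. They do not support concluding that the significant differences reported under Limitations and Caveats are artefacts. That passage refers to laryngeal responsiveness, and the primary outcome lies outside this problem. The check is worth making because it is cheap.

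**What to change.** 1. Tabulate the anchor filament (6-0, 5-0, 4.5-0, 4-0) by group.
2. If any subject was anchored above 6-0, add a sensitivity analysis of the ratings: a rank test stratified by anchor (van Elteren), collapsed to 6-0 v heavier if strata are sparse, or the same comparison restricted to 6-0-anchored subjects.
3. Report it beside the main test, with estimates as well as p-values. If the anchor mix differs and the estimate changes materially, describe the rating difference as possibly due to the reference. Loss of significance alone should not discard a difference, given the power lost.
4. If the anchor filament was not recorded (the documents do not say), state that as a limitation on the rating comparison.

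The cost is one table and one supplementary analysis, with no new testing and no change to the primary outcome. The drawbacks are lower power and sparse strata with 13 AdLD subjects. Restriction also selects subjects by sensitivity, and stratifying reduces the bias but may not remove it.

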Sixteen subjects with AdLD were identified and recruited; 3 subjects could not complete laryngopharyngeal testing. Thirteen total subjects were included in analysis (mean age 60+/-15.2 years, 9 women). Patient demographics are outlined in Table above. The healthy control cohort comprised 33 individuals, 36% female (n=12) with a mean age of 52 +/- 18.1 years.

3. Outcome Measures (as specified in the study record)

Primary outcome measure was the presence or absence of the Laryngeal Adductor Reflex (LAR) as observed via flexible laryngoscopy. A previously validated, standardized protocol was utilized to

stimulate the larynx in 3 distinct anatomic sites (lateral pyriform sinus (LPS), aryepiglottic fold (AEF), and false vocal folds (FVF)), with a series of monofilaments of increasing size/force: 6-0, 5-0, 4.5-0 and 4-0 monofilaments.

Additional outcome measure included subjective perceptual strength rating, as reported by the patient, on a scale of 1-10.

4. Adverse Events: none

5. Limitations and Caveats

Results of this study showed statistically significant differences in laryngeal responsiveness between AdLD and normal cohorts. However, these results may have limited generalizability beyond AdLD (i.e., to abductor-type LD, mixed LD, or isolated essential tremor). The impact of concurrent essential tremor on results could not be assessed in this small study. This study is also limited by the non-randomized nature of testing protocol (although the rationale for this protocol has been described previously in the literature) and the unknown effects of BtxA dose or timing on laryngeal sensation testing results. Future, prospective, larger-scale, ideally multi-institutional studies are needed to explore the findings of this study further.

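### FVF strength ratings above the 6-0 filament exist only for subjects with no earlier observed FVF reflex, so those group contrasts are selected on the primary outcome (minor)

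*Combined protocol and SAP*

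**What the plan says.** Under Laryngopharyngeal Sensory Evaluation, the lateral pyriform sinus (LPS) and aryepiglottic fold (AEF) go through the whole series after 6-0: "The LPS and AEF were tested in order of increasing stimulus: 5-0, 4.5-0 and 4-0 monofilaments". The FVF follow a different rule: "Testing of FVF terminated after the first observed LAR given site sensitivity, assuming positive responses would also be present for increased monofilament strength".

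The same section describes how a rating arises: "Participants were instructed to raise their hand when the stimulus was detected, and then were asked" to score the stimulus against the nasopharyngeal anchor. No delivered and detected stimulus means no score.

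The stopping decision is made live, but the reflex is settled later. LAR Assessment says: "Confirmation of LAR was determined using post-hoc frame-by-frame analysis of video recordings". Stimuli can also be excluded at that review.

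Under Statistical Methods, Mann-Whitney and Fisher exact tests were "used to compare strength ratings and LAR rates between AdLD and control groups at specific sites and filament sizes". No exception for FVF is visible. In the text available for this review the section breaks off at "To assess predictors of LAR, subjective detection, and", so the rest of the method could not be read.

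Outcome Measures makes presence or absence of LAR the primary outcome, over three sites and four filaments. It then adds: "Additional outcome measure included subjective perceptual strength rating, as reported by the patient, on a scale of 1-10".

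**The concern.** Three of the 12 site-by-filament cells (FVF at 5-0, 4.5-0 and 4-0) do not hold the same kind of data as the other nine.

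- **Ratings.** Anyone with an observed FVF LAR drops out of all later FVF ratings. Those left are the less reflexive members of each group. If one group is more reflexive and reflexive people tend to rate stimuli as stronger, the two remaining sets are not comparable, even when the groups rate stimuli identically. The sets may also be small.
- **LAR.** Above 6-0, an earlier responder's positive is assumed. If these are counted, the FVF rate is a cumulative one (LAR at that filament or a weaker one). It equals the filament's own rate only if nobody who responds to a weaker filament fails to respond to a stronger one.

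Monotonicity would settle the LAR part. It does nothing for the ratings, because no assumption supplies a score for a stimulus that was never delivered.

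**Working it through.** The documents give no power, alpha, FVF rate or rating SD bearing on this point, so there is no plan figure to reproduce. The selection itself follows from the text alone. Its size needs assumptions.

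**Inputs.** From the document: 13 AdLD subjects and 33 controls. Assumed: control LAR rates at 6-0/5-0/4.5-0/4-0 of 30/40/50/60% (low) or 70/80/88/95% (high); within-person correlation r = 0.5 unless stated; AdLD shifted by s SD on the reflex scale; rating loading w = 0.3 or 0.6 on the shared sensitivity; no true group difference in rating. The model is latent normal: LAR at filament k when √r·u + √(1−r)·e + s exceeds the cut-point c for the assumed rate, and rating = w·u + noise with total SD 1.

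**1. How many can be rated.** At 5-0 the most that can remain, with the same rate in both groups, is n × (1 − rate at 6-0).
- 30% respond at 6-0: 13 × 0.7 = 9.1 and 33 × 0.7 = 23.1.
- 70% respond: 13 × 0.3 = 3.9 and 33 × 0.3 = 9.9.
- At 4-0, by simulation: 4.4 and 11.1 (low), 0.6 and 1.5 (high).

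These are upper limits, since undetected and excluded stimuli reduce them further.

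**2. Rating bias (AdLD minus control).** At 5-0 it has a closed form: bias = −w·√r·[λ(c − s) − λ(c)], where λ(x) = φ(x)/Φ(x).
- Low rates, c = 0.524, λ(c) = 0.497.
- s = 0.5: λ(0.024) = 0.782, so bias = −w × 0.707 × 0.286 = −0.06 (w = 0.3) or −0.12 (w = 0.6).
- s = 1.0: λ(−0.476) = 1.123, so bias = −w × 0.707 × 0.627 = −0.13 or −0.27.

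Beyond 5-0 it was simulated. For w = 0.6, in SD at 5-0/4.5-0/4-0:

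| AdLD shift | Low rates | High rates |
|---|---|---|
| +0.5 SD | −0.12/−0.18/−0.21 | −0.16/−0.22/−0.26 |
| +1.0 SD | −0.27/−0.38/−0.45 | −0.34/−0.46/about −0.5 |
| −1.0 SD | +0.15/+0.25/+0.33 | +0.27/+0.39/+0.46 |

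The bias is proportional to w, so w = 0.3 halves every entry. It is zero if s = 0 or w = 0. In the high-rate 4-0 cell at +1.0 SD almost no AdLD subject remains, so that entry is only nominal. Over simulated trials of 13 against 33, the Mann-Whitney false-positive rate stayed between 0% and 7%.

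**3. LAR contrast.** Bias = (difference in carried-forward rates) − (difference in per-filament rates), in percentage points at 5-0/4.5-0/4-0, r = 0.5:
- Low, +0.5 SD: +0.8/−1.6/−4.2.
- Low, +1.0 SD: −1.3/−6.3/−9.9.
- Low, −1.0 SD: −6.9/−8.0/−5.4.
- High, +1.0 SD: −6.2/−6.3/−3.3.
- High, −1.0 SD: +2.0/+6.8/+7.7.

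At r = 0.9 every entry is under 2 points. With no group difference, or with monotone responses, it is zero. For scale, in the low-rate setting at 4-0 and +1.0 SD, the per-filament rates are 89.5% and 60%, a difference of 29.5 points, and the carried-forward difference is 29.5 − 9.9 = 19.6. The bias is toward no difference in most settings. The main exception is low rates with AdLD less reflexive, where it widens the gap.

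**4. What a monotonicity check would show.** Share of subjects with an LAR at one filament and a negative at a stronger one: 0% if monotone; 9% (low) or 4% (high) at r = 0.9; 20% or 10% at 0.75; 33% or 17% at 0.5.

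**The case against.** The strongest reply concerns LAR. The convention is disclosed with a reason, and it is plausible, because the 6-0, 5-0 and 4-0 filaments "deliver an increasing mean force of 0.03 g, 0.11 g, and 0.30 g". It applies to both groups. A reader might take the within-group excess (11, 16 and 18 points at 5-0, 4.5-0 and 4-0 under the low rates and r = 0.5) as the error in the result. It is not: the plan compares groups, much of that excess cancels, and with no group difference all of it does. A carried-forward positive at a filament is also the same datum as a threshold at or below it, so replacing the Fisher tests with one threshold test is a preference rather than a correction. This part of the reply stands.

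It is also fair that sparsity is not established. Under the low rates about 9 and 23 subjects could still be rated at 5-0. Nor can it be said that the plan fails to deal with the untested cells, since part of Statistical Methods was not available. Whether those cells were tested, and whether assumed positives were counted, is a question for the sponsor. But missing text cannot create ratings for stimuli that were not delivered, so the selection of FVF ratings remains.

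A reader might also infer that the group differences reported under Limitations and Caveats arise from this rule. The documents do not support that: the statement names neither site nor direction.

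**Conclusion.** The point holds as a minor one, mainly for ratings. FVF ratings at 5-0, 4.5-0 and 4-0 are conditional on no earlier observed FVF LAR, and any group test on them is selected on the primary outcome.

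On assumed inputs with within-person correlation 0.5, the bias if AdLD is 0.5 to 1.0 SD more reflexive runs from about −0.06 to −0.25 SD at the weaker reflex-rating link and from about −0.12 to −0.5 SD at the stronger one. The sign reverses if AdLD is less reflexive. The harm is a shifted and possibly sparse contrast, not a flood of false positives.

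For LAR, the between-group bias is at most about 10 points at correlation 0.5 and under 2 points at 0.9. The actual size and direction cannot be determined, because the text gives neither FVF response rates nor the link between rating and reflex.

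**What to change.** Leave testing as it is and change the analysis and labels.

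1. Make 6-0 the main FVF rating comparison, because no subject can have been stopped before it. State that it is still conditional on detection, and give the number in each group who detected the stimulus. Report FVF ratings at stronger filaments descriptively, labelled as conditional on no earlier observed FVF LAR, with n per group.
2. Label FVF LAR above 6-0 as cumulative (LAR at that filament or a weaker one), and state whether assumed positives entered the Fisher tests. If the LAR that ended testing is excluded or overturned on video review, treat the stronger filaments as not tested for that subject.
3. Check monotonicity by group in the LPS and AEF data already collected: the share of subjects with a confirmed LAR at one filament and a valid negative at a stronger one. Say that the check is indirect, because FVF itself was not tested past the first LAR.

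A single FVF threshold outcome with one rank test is an optional alternative. The cost is some SAP wording and a small re-analysis of existing data. The loss is that FVF ratings above 6-0 become descriptive.
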